External validation is essential to support the general applicability of developed scores. External validation studies may address aspects of geographical and clinical spectrum transportability. Ideally this should be done using a reference standard, but this is practically lacking in childhood TB (the gold standard, mycobacterial culture, being inadequately sensitive). To classify children as unconfirmed or unlikely TB cases, the recently updated international consensus Clinical Case Definitions for Classification of Intrathoracic Tuberculosis in Children is highly dependent upon the clinician's decision to treat [59]. This reference standard would therefore not be independent from the PAANTHER TB treatment decision algorithm, which would lead to major incorporation bias in the estimation of the algorithm diagnostic accuracy. The option of a diagnostic clinical trial in primary and secondary healthcare facilities would bring high quality evidence but raises major logistical issues.

We will therefore proceed to an external validation of the PAANTHER prediction model in new populations of HIV-infected children from four high TB burden countries in Africa to examine its robustness and transportability to other geographical, epidemiological and health care settings, using a "management study" design. This type of design has been largely used in pulmonary embolism diagnostic studies, where the potentially iatrogenic reference standard cannot be applied to all patients [60], [61].

With such a design, our study will focus on the evaluation of the safety of withholding TB treatment in HIV-infected children with presumptive TB based on a negative result for the PAANTHER treatment decision algorithm, which will be substituted to routine clinical care at baseline, except in children with severe/life threatening conditions for whom TB treatment decision could be made at the discretion of the site clinician. All children will be prospectively followed-up and monitored, especially those not initiated on treatment as per the PAANTHER

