3.2. Secondary study endpoints

1. Time to final TB treatment decision and proportion of children with presumptive TB having completed the PAANTHER TB-treatment decision algorithm

The algorithm will be considered completed if a decision to initiate TB treatment has been taken at any step of the algorithm or if TB has been excluded after systematic evaluation, and all steps planned in the algorithm have been implemented.

 Proportion of cases considered as unlikely TB by the Expert Committee in those initiated on treatment as per the PAANTHER TB treatment decision algorithm (false positive) 3.

- a. Morbidity (drug-induced toxicity ART and TB treatment-related, opportunistic infections, IRIS), with or without TB treatment, and mortality at 6 months
- b. Time to ART initiation in ART-naïve children
- c. CD4 (absolute count and %) gain
- 4. Weight gain at 6 months (absolute value and percentage of body weight), TB symptoms resolution and outcomes in children on TB treatment
- 5. Time to IPT initiation and proportion of children initiated on IPT in those not initiated on treatment as per PAANTHER TB treatment decision algorithm
- Discrimination (area under the receiver-operating-characteristic curves [AUROC]) and calibration measures of the PAANTHER prediction model including or not MLR and CRP, against the TB composite reference standard as defined by the Expert Committee
- 7. Proportion of NPAs (or sputum) and stool samples with *mycobacterium tuberculosis* (MTB) detected using Ultra
- 8. Feasibility defined as proportion of children with NPA and stool samples collected as per study protocol

Safety defined as proportion of NPA with AEs (vomiting, nose bleeding, low oxygen saturation, respiratory distress) occurring during NPA and

Tolerability defined as discomfort/pain/distress experienced by the child during NPA as assessed by the child (Wong-Baker face scale), by the parents (visual analog scale), by the nurses (FLACC behavioral scale) (quantitative assessment) in a subset of children

- Diagnostic accuracy (false negative and false positive rates i.e. NPV and PPV and corresponding sensitivity and positivity) of the PAANTHER algorithm in the different subgroups in terms of age, CD4 counts, nutritional statuses, and timings of ART initiation (on/off ART)
- 10. Incremental cost-effectiveness ratio (ICER)

3.3. Reference diagnosis/case definitions and validation by the Endpoint Review Committee and the international Expert Committee

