An Endpoint Review Committee will be set up at the national level for the purpose of case review and validation of TB diagnosis. The national Endpoint Review Committee will review and validate all new TB cases in children initially non-treated for TB, using the updated Clinical Case Definitions for Classification of Intrathoracic Tuberculosis in Children (see Table 2). The Endpoint Review Committee will also validate differential clinical and other diagnoses on opportunistic infections and adverse events. All reviews will be performed following Standard Operating Procedures (SOPs) specifically developed for the study.

Additionally, at the international level, an Expert Committee will be set up for the purpose of clinical validation of TB diagnosis, including identification of children with unlikely TB in those initiated on treatment as per the PAANTHER TB treatment decision algorithm. The International Expert Committee will validate final TB diagnosis and will determine, based on timing, clinical features, and any other relevant information whether missed TB cases are false negatives, potential TB unmasking IRIS or new TB infections. The use of the updated Clinical Case Definitions for Classification of Intrathoracic Tuberculosis in Children will not be possible as treatment decision is not clinician based but algorithm-guided. The Expert Committee will also review part of all cases reviewed at country level to ensure homogeneity of classification across countries (See figure 2).

The Clinical Case Definitions for Classification of Intrathoracic Tuberculosis in Children were initially developed for children with suspected TB and may not be fully relevant for children with HIV infection [59]. They may be revised by the Scientific Advisory Board (SAB) based on current state of the art on time of final case review.

For the purpose of reference diagnosis and case definition, CXRs will be read by 2 independent experts experienced in reviewing CXRs in children, blinded to all of the clinical information and to each other's interpretation. In case of disagreement, advice from a third expert will be sought. For routine care, CXR will be read by the site clinician.

 Table 2. Updated Clinical Case Definitions for Classification of Intrathoracic Tuberculosis in

 Children (adapted from Graham et al, 2015 [59])

| Case definition | Refined criteria | | | |
|-----------------------------|---|--|--|--|

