11.2.3. Analysis of secondary endpoints

The median time to TB treatment decision and interquartile range, and the proportion of children with presumptive TB having completed the PAANTHER TB treatment decision algorithm will be estimated.

We will assess the proportion of HIV-infected children with unlikely TB among those initiated on treatment as per the PAANTHER TB treatment decision algorithm (false positive cases) identified by the international Expert Committee. We will estimate the positive predictive value (PPV) and its 95% confidence intervall. Once PPV and NPV are assessed, we will estimate sensitivity and specificity of the algorithm/scoring system and TB prevalence.

Discrimination and calibration, which are key measures of a model's predictive performance, will be quantified for the original model and the model incorporating new predictors. To avoid adding optimism, the original model will not be redeveloped. Discrimination of the model, measured by the C statistic, or area under the receiver operating characteristic (AUROC) curve, will be estimated for the original model and parameters with and without potential new predictors such as MLR and CRP. AUCs of the models will be compared using bootstrapping technique. Calibration examines the agreement between predicted and observed risk of disease and can be quantified by a calibration slope and the expected/observed (E/O) statistic (ratio of the total expected to have disease to the total observed with disease). TB diagnosis as assessed through the Expert Committee review of false negative and false positive cases will be used as reference standard.

Sensitivity analyses will be conducted to assess impact of age, ART, CD4, and nutritional status on the performance of the score. Furthermore, the score will be assessed country-wise to identify potential heterogeneity in score performances between countries.

If a lower predictive accuracy is found, we will update the existing prediction model and adjust or recalibrate it to the validation sample. As a result, the updated model combining the information from the original PAANTHER model with new information from the TB-Speed study, will probably have improved transportability to other populations.

Sensitivity, specificity, and predictive values of Ultra in NPA and stool will be measured for each specimen independently and for the combination of the 2 specimens against mycobacterial culture.

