13.5. Expert Committee

At the international level, the expert committee will consist of 3 to 4 independent experts not involved in the management of the study, nor members of the SAB. The expert committee will clinically validate final TB diagnosis. They will have access to CXR external reviews.

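### Secondary endpoint 6 tests the added value of MLR and CRP against an Expert Committee diagnosis that is not shielded from CRP or the blood count

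*Protocol*

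**What the plan says.** Endpoint 6 in Section 3.2 compares the PAANTHER model "including or not MLR and CRP, against the TB composite reference standard as defined by the Expert Committee". Section 11.2.3 repeats the choice of yardstick: "TB diagnosis as assessed through the Expert Committee review of false negative and false positive cases will be used as reference standard". For the comparison itself it says "AUCs of the models will be compared using bootstrapping technique".

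Section 3.3 describes how the committee reaches its diagnosis. It first removes the usual tool: "The use of the updated Clinical Case Definitions for Classification of Intrathoracic Tuberculosis in Children will not be possible", because treatment follows the algorithm and not the clinician. It then asks the committee to determine, "based on timing, clinical features, and any other relevant information whether missed TB cases are false negatives", unmasking IRIS or new infections. For children treated on the algorithm, the committee is to identify those with unlikely TB, and no basis for that judgement is given.

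Blinding is stated for one party only. The two chest X-ray readers are "blinded to all of the clinical information" in Section 3.3, and Section 8.3 extends this to biological data. Section 13.5 says of the Expert Committee only what it receives: "They will have access to CXR external reviews".

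**The concern.** When the reference diagnosis can draw on a marker, that marker's accuracy against the reference is partly agreement with itself. A marker with no relation to TB could then appear to add discrimination, and calibration of the extended model would be judged against the same contaminated label. Bootstrapping the AUC difference does not help, because it measures sampling variation and takes the label as given.

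Section 4.2 says the committee's review will serve to assess MLR and CRP and, if needed, to propose a new version of the score. A spurious gain could therefore end up in the tool. A statistical analysis plan cannot repair this later: once the committee has classified a child with the CRP value in view, its influence cannot be taken out.

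**Working it through.** The plan gives no figure on this point, so there is none to reproduce. The check is a reading of the text, followed by an illustration.

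**Could the markers reach the committee?**
- CRP and the complete blood count are taken at D0, M2 and M6 (Sections 7.3, 7.7 and 8.1), so the values are in the record.
- Section 6.2 trains site staff to interpret MLR and CRP among the TB assessment procedures. The protocol thus treats them as evidence on TB.
- MLR is calculated secondarily (Section 8.2.3). The ratio may not be on file at review, but its two components are. CRP is the more direct route.

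**Does anything keep them out?**
- Table 2 contains neither CRP nor MLR and would have kept them out. Section 3.3 says the Expert Committee cannot use it.
- No substitute criteria are listed.
- No section withholds CRP or the blood count from the committee.

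The route is therefore open. The protocol does not say that it will be used.

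**What could it do?** The following is hypothetical; none of the inputs comes from the protocol. There are 400,000 simulated children per scenario, with true TB status D at 50% prevalence. Score S is normal with mean 1.1·D, other evidence E has mean 2·D, and the marker M has mean μ·D, each with SD 1. The committee forms L = E + w·M + v·S and calls TB when L exceeds its median. The apparent gain is AUC(S and M) minus AUC(S) against that label. The true gain is the same difference against D.

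| μ | w | apparent gain, v = 0 | apparent gain, v = 0.5 | true gain |
|---|---|---|---|---|
| 0 | 0 | 0.000 | 0.000 | 0.000 |
| 0 | 0.25 | 0.011 | 0.005 | 0.000 |
| 0 | 0.5 | 0.045 | 0.021 | 0.000 |
| 0 | 1 | 0.148 | 0.082 | 0.000 |
| 0.5 | 0 | 0.015 | 0.009 | about 0.022 |
| 0.5 | 0.25 | 0.046 | 0.026 | about 0.022 |
| 0.5 | 0.5 | 0.084 | 0.049 | about 0.022 |

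The table shows two things. A marker with no value (μ = 0) gains as soon as w is above zero. When score items also enter the reference (v = 0.5), the apparent gain is smaller, because the score's own AUC rises (from 0.693 to 0.807 at μ = 0, w = 0). For a marker with real value, the result can then fall below the truth (0.009 against 0.022) or above it (0.049 against 0.022), depending on w.

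**The case against.** The strongest reply is that the open wording in Section 3.3 has a narrow job. It governs how missed cases already found are sorted into false negatives, unmasking IRIS and new infections. A reader might infer that it licenses the committee to use anything at all for TB versus no TB across the cohort; the text does not say that. MLR and CRP are not named as committee inputs anywhere. This stands, and it is why the point can only be put as a possibility. It does not close the gap, because for unlikely TB in treated children no basis is stated, which is no tighter.

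Second, Section 3.3 refers to standard operating procedures for the reviews. They are not shown and might limit the dossier. The sentence follows the description of the national committee, so its reach to the Expert Committee is arguable, and the protocol states no such limit.

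Third, national review of new cases in initially untreated children does use Table 2, which is free of both markers. That is a partial safeguard for one group. The Expert Committee still gives the final diagnosis.

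Fourth, a reader might take the Introduction's warning about a reference "which would lead to major incorporation bias in the estimation of the algorithm diagnostic accuracy" as the protocol's own verdict on these markers. It is not. It concerns a reference that depends on the clinician's decision to treat. It shows only that the authors know the mechanism.

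Fifth, a reader might want the PAANTHER total hidden as well, to protect the score's own accuracy. That would achieve little: symptoms, X-ray and bacteriology must stay visible, they make up most of the score, and treatment status shows the algorithm's decision.

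**Conclusion.** The concern holds as a possible bias in one secondary endpoint. The reference standard for endpoint 6 is not protected from CRP or from the counts behind MLR, so the measured added value of these markers may be biased.

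The size is unknown. It depends on what the committee is shown and how much weight it gives, and the protocol states neither. The simulated gains illustrate the mechanism and should not be quoted as an estimate for this study. The net direction is also uncertain if score items enter the reference.

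A reader might infer that the primary analysis is compromised too. This point does not support that: it concerns the comparison of models with and without MLR and CRP, and leaves the primary NPV and its 75% criterion untouched.

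**What to change.** In Sections 3.3 and 13.5, state that the Expert Committee records its reference classification (TB or unlikely TB) for each child before it sees CRP, MLR or the monocyte and lymphocyte counts, and that these may be unsealed only afterwards. Endpoint 6 should use the classification recorded first.

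This takes one sentence in each section and a dossier template with those values removed. It changes no visit, sample or sample size. The cost is that the committee lacks these values as an aid at the first classification, which may matter in some children with competing diagnoses. They remain available once the classification is recorded.

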7.10. Management in the case of selected adverse events

7.10.1. Management in the case of sample collection adverse events

Expected AEs occurring from NPA collection procedure include, by decreasing order of frequency: cough (this induced cough reflex is expected as it is the mechanism by which sample is obtained), nausea, local trauma/nose bleeding, sneezing, vomiting, and in rare cases dyspnea/low O2 saturation and heart rate deceleration <60/mm [32].

NPA will be performed by study nurses under SpO2 monitoring. In case of acute O_2 desaturation or respiratory distress occurring during sample collection, the procedure will be immediately interrupted and the child will be started on O_2 therapy. If a sample could not be obtained, a new attempt will be performed as soon as the child respiratory status allows for it.

Management in case of AEs will be detailed in specific SOPs.

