8.2. Laboratory assessment

8.2.1. TB bacteriological tests

The Ultra assay will be performed within 3 days of inclusion (D0-D2) on the following samples:

- one untreated NPA
- one stool sample with prior processing
- two GAs (or expectorated sputum)

The Ultra assay will be done at the hospital laboratory on standard G4 platforms.

The Ultra assay will be carried out according to the manufacturers' guidelines and will be defined as positive, negative or indeterminate based on the manufacturers' recommended criteria.

Results will be interpreted as follows:

- In case of positive result for the presence of MTB (including "trace call" positive result) on any sample, the global result will be given as "detected".
- In case of negativity of Ultra performed on all samples, the global result will be given as "not detected".
- In case of an invalid or error result for MTB detection, the test will be repeated if sample volumes allow for it.

If volumes are insufficient to repeat testing, no additional sample will be collected unless the child has symptoms or signs suggestive of TB (persistent cough or fever for more than 2 weeks, and failure of antibiotics treatment). The child will be evaluated for TB using routine sample collection (gastric aspirate or other sample according to country practices) for Ultra testing, as recommended by WHO.

• In case of rifampicin resistance detected on one or more sample, the result will be given as "MTB detected, rifampicin resistance detected". Otherwise the result will be given

as "MTB detected, rifampicin resistance not detected (or indeterminate)". Children with rifampicin resistance detected by Ultra will have culture and phenotypic DST performed on leftovers from NPAs and stool (and additional samples if needed), and will be started on empirical MDR-TB treatment.

Ultra results will be communicated by the laboratory to the nurse or clinician as soon as the result is available.

Leftover of NPAs, stool samples, and GA or sputum will be kept at -80°C for future ancillary/sub-studies.

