9.2. Expected adverse events related to the study intervention

Expected AEs occurring from NPA collection procedure include, by decreasing order of frequency: cough (this induced cough reflex is expected as it is the mechanism by which sample is obtained), nausea, local trauma/nose bleeding, sneezing, vomiting, and in rare cases dyspnea/low O2 saturation and heart rate deceleration <60/mm [32].

No AEs are expected from stool sample collection.

Overall, children tolerate anti-TB drugs very well when using currently recommended dosages. SAEs are rare and even mild symptoms such as nausea or vomiting are uncommon. There are occasional case reports of severe hepatotoxicity [68].

Occurrence of AEs will be monitored by study nurses and reported in the Case Report Form (CRF). Management in case of AEs will be detailed in clinical SOPs (see chapter 7.7.1).

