Primary endpoint:

Proportion of missed TB cases (false negative cases) in children not initiated on treatment as per the PAANTHER TB treatment decision algorithm

Secondary endpoints:

1.Time to final TB-treatment decision and proportion of children with presumptive TB having completed the PAANTHER TB treatment decision algorithm.

The algorithm will be considered completed if a decision to initiate TB treatment has been taken at any step of the algorithm or if TB has been excluded after systematic evaluation, and all steps planned in the algorithm have been implemented.

2. Proportion of cases considered as unlikely TB by the Expert Committee in those initiated on treatment as per the PAANTHER TB treatment decision algorithm (false positive)

3. a. Morbidity (drug-induced toxicity – ART and TB treatment-related, opportunistic infections, IRIS) with or without TB treatment, and mortality at 6 months;

b. Time to ART initiation in ART-naïve children;

c. CD4 (absolute count and %) gain.

4. Weight gain at 6 months (absolute value and percentage of body weight), TB symptoms resolution and outcomes in children on TB treatment

5. Time to IPT initiation and proportion of children initiated on IPT in those not initiated on treatment as per PAANTHER TB treatment decision algorithm

6. Discrimination (area under the receiver-operating-characteristic curves [AUROC]) and calibration measures of the PAANTHER prediction model including or not MLR and CRP, against the TB composite reference standard as defined by the Expert Committee

7. Proportion of NPAs (or sputum) and stool samples with positive TB detection using Ultra

8. Feasibility defined as proportion of children with NPA and stool samples collected as per study protocol;

Safety defined as proportion of NPA with AEs (vomiting, nose bleeding, low oxygen saturation, respiratory distress) occurring during NPA, and

Tolerability defined as discomfort/pain/distress experienced by the child during NPA as assessed by the child (Wong-Baker face scale), by the parents (visual analog scale), by the nurses (FLACC behavioural scale) (quantitative assessment) in a subset of children

9. Diagnostic accuracy (false negative and false positive rates i.e. NPV and PPV and corresponding sensitivity and positivity) of the PAANTHER algorithm in the different subgroups in terms of age, CD4 counts, nutritional statuses, and timings of ART initiation (on/off ART)

10. Incremental cost-effectiveness ratio (ICER)

Study design:

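### The NPA safety endpoint uses a closed list of four events that omits heart-rate deceleration, which the protocol itself names as an expected rare reaction to the procedure (minor)

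*Protocol*

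**What the plan says.** Section 3.2, endpoint 8, gives the safety part of the NPA assessment as "Safety defined as proportion of NPA with AEs (vomiting, nose bleeding, low oxygen saturation, respiratory distress) occurring during NPA". The protocol summary in Appendix 1 gives the same four events and the same unit. Neither place says that the bracket only illustrates.

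Sections 7.10.1 and 9.2 carry a longer list of reactions expected from the procedure. It runs from common ones (cough, nausea, local trauma or nosebleed, sneezing, vomiting) to uncommon ones: "in rare cases dyspnea/low O2 saturation and heart rate deceleration <60/mm".

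On conduct, section 7.10.1 states "NPA will be performed by study nurses under SpO2 monitoring". After acute desaturation or "respiratory distress occurring during sample collection, the procedure will be immediately interrupted". It adds: "If a sample could not be obtained, a new attempt will be performed as soon as the child respiratory status allows for it".

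On recording, section 9.2 has nurses monitor these reactions and enter them in the CRF. Section 9.3 extends CRF reporting to all adverse events, including those from NPA collection. Section 9.4 requires notification to the sponsor of serious events related to NPA collection.

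**The concern.** An endpoint defined by a closed list measures only what is on the list. The protocol names two rare reactions to the procedure side by side and puts one in the endpoint and not the other. A nurse could record an isolated fall in heart rate in the CRF, and the analyst applying section 3.2 would still classify that NPA as having had no adverse event.

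Safety of NPA collection is a named secondary objective (section 2.2, objective 8). What is at stake is whether its one defined proportion covers the reactions that the protocol says to expect. The omission can only push that proportion down.

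**Working it through.** The protocol states no expected rate or precision for NPA safety, so there is no figure to reproduce. The check is a comparison of texts, followed by an illustration under assumed rates.

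**Step 1: compare the lists.**

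| Reaction | Expected (7.10.1, 9.2) | Endpoint 8 (3.2, Appendix 1) |
|---|---|---|
| Cough | yes | no |
| Nausea | yes | no |
| Sneezing | yes | no |
| Nosebleed | yes | yes |
| Vomiting | yes | yes |
| Dyspnea / low saturation | yes, rare | yes (as low saturation and respiratory distress) |
| Heart-rate deceleration | yes, rare | **no** |

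The protocol explains that cough is how the sample is obtained, so leaving it out is understandable. Nausea and sneezing are mild. Neither reason fits heart-rate deceleration: the endpoint keeps vomiting and nosebleeds, and it keeps the other rare reaction.

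**Step 2: how many events could be missed.** Inputs: 550 children (sections 4.3 and 6.3) and one NPA planned per child (section 7.4). The rate r of isolated heart-rate deceleration is an assumption.

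Expected missed events = 550 × r; chance of at least one = 1 − (1 − r)^550.

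| Assumed r | Expected events | Chance of at least one |
|---|---|---|
| 0.2% | 550 × 0.002 = 1.1 | 0.67 |
| 0.5% | 550 × 0.005 = 2.75 | 0.94 |
| 1% | 550 × 0.01 = 5.5 | 0.996 |

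The reported proportion is too low by at most r, that is 0.2 to 1 percentage point. A child who also has a listed event is already counted, so any overlap makes the shortfall smaller.

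**Step 3: does the unit matter?** The protocol uses NPA for the procedure ("NPA will be performed by study nurses under SpO2 monitoring") and for the specimen ("one untreated NPA"). Assume 28 procedures with other listed events (about 5% of 550) and 3, 6 or 11 interrupted attempts, each with a listed event and no sample, all repeated later without an event.

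- Per attempt: 31/553 = 5.6%, 34/556 = 6.1%, 39/561 = 7.0%.
- Per child: 31/550 = 5.6%, 34/550 = 6.2%, 39/550 = 7.1%.
- Only attempts that yield a specimen: 28/550 = 5.1% in each case.

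Attempts and children give almost the same answer. Only a specimen-based count would lose events, and no section prescribes one.

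**The case against.** The strongest reply is that nothing is lost from the trial's safety data. Section 7.4 refers to section 9.2 for NPA adverse events, section 9.1 grades their severity, section 9.3 puts all adverse events in the CRF, and section 9.4 has serious ones notified. This stands: participant protection does not depend on endpoint 8. It does not repair the endpoint, which as worded still excludes the event from the reported proportion.

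A second reply is that the bracket was never meant to mirror section 9.2, since cough, nausea and sneezing are absent too, and that choosing events for a summary proportion is a design choice. That is fair in general, but the protocol gives no reason that would cover heart-rate deceleration. Nor is this a detail left to the statistical analysis plan, because the protocol fixes the list itself in two places.

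A reader might go further and infer that interrupted attempts fall out of the count, so that the most serious reactions disappear. The text does not support this:

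- The endpoint counts events occurring during NPA, which describes the procedure.
- Both triggers for interruption, desaturation and respiratory distress, are on the endpoint list.
- Section 7.10.1 makes the new attempt conditional: "If a sample could not be obtained, a new attempt will be performed as soon as the child respiratory status allows for it". An interrupted attempt may therefore still yield a sample.
- The choice between attempts and children can be left to the analysis plan, which section 11.2.3 says will detail the secondary endpoints.

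A reader might also take objective 8 as a claim of safety at lower levels of care. It concerns NPA collection in HIV-infected children; the wider ambition is stated for the algorithm. Finally, the protocol calls heart-rate deceleration rare, not serious, so no statement that a serious-event figure would change severalfold can be drawn from it.

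**Conclusion.** The point holds as a minor correction to one descriptive secondary endpoint. Endpoint 8 leaves out a reaction that sections 7.10.1 and 9.2 both list as expected, and read literally it classes an NPA with isolated heart-rate deceleration as having no adverse event.

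The effect is a slightly low proportion of unknown size. The range of about 1 to 6 events in 550 rests wholly on assumed rates of 0.2% to 1%, on one NPA per child, and on no overlap with listed events. The primary endpoint, the sample size and safety oversight are not affected. The unit of count is worth a clarifying phrase but is not an error.

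**What to change.** In section 3.2 (endpoint 8) and Appendix 1, add heart-rate deceleration, as sections 7.10.1 and 9.2 define it, as a fifth item in the bracket. As a clarification only, add that an NPA here means each procedure attempted, including those interrupted.

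The cost is a wording change in two places. The adverse-event data are already required by sections 9.2 and 9.3. The protocol mentions only oxygen-saturation monitoring during the procedure, so the team should confirm that the NPA form in the eCRF records heart-rate deceleration. The downside is that the reported adverse-event proportion may be slightly higher.
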